9.2 Planned recruitment rate

The selection of the participating Early Pregnancy Units was completed in April 2016. Each unit will collect data until a total of 150 patients have been recruited and for minimum seven days. Units will start and finish collecting data at different times (staggered data collection) and data will be collected over approximately six months.

9.3 Statistical analysis plan

9.3.1 Primary outcome analysis – Cohort study of clinical outcomes

The primary analysis will investigate whether consultant presence is associated with admission rate. We will perform a patient-level analysis and hence will use hierarchical logistic regression models that allow for patient clustering within EPAUs. Consultant

presence will be modelled as a continuous variable. The use of regression modelling will allow us to adjust for confounding factors, which may be associated with higher admission rates. The results of this analysis will be reported in terms of odds ratios (with corresponding confidence intervals and P-values) to indicate the degree of association. All model assumptions will be checked. Specifically, level 2 residuals will be checked for normality and linearity assumptions will be checked. The ICC, which indicates the degree of clustering within EPAUs, will also be reported. Multiple imputation will be used if there is a high degree of missing data.

Regarding analysis, our first step will be to characterize the amount of missing data and to identify patterns of missingness, if they exist. Simple descriptive analyses will be used to describe the missingness of each (important) variable, then tabulations and logistic regression modelling will be used to explore whether the missingness in one variable depends on specific patient characteristics. These analyses may give us an insight into whether we can assume that the data are 'missing at random'. Under a 'missing at random' (MAR) assumption, we may model the data, taking account (adjusting) of those variables associated with missingness. This will lead to valid inferences (if our MAR assumption is correct). In addition, we will consider using multiple imputation methods to impute the missing values. This will be achieved by using 'imputation via chained equations'²⁰. Under a MAR assumption, this method imputes missing values (using regression models) based on the values of other variables. Multiple imputed datasets are produced to account for the uncertainty involved in the imputation process. These datasets are then analysed separately and the results combined. It is likely that these imputation models will make use of the clinical data, which are expected to be near complete. If the 'missing at random' assumption is thought to be untenable, we will use a few approaches to deal with this issue. Firstly, though, it will be important to understand the possible reasons for the missing values to better design the sensitivity analyses that follow. Then, we will investigate the use of relatively complex imputation models as part of the multiple imputation exercise. The idea here is that by including more variables in the imputation model, the MAR assumption should become more plausible²⁰. We will also use sensitivity analyses to check the robustness of our results. Specifically, we will impute the missing data under various ('missing not at random') scenarios and see how the results of our primary analyses change.

9.3.2 Secondary outcome analysis

The analyses of the secondary outcomes (number of follow-up visits, non-diagnostic ultrasound scans, negative laparoscopies, estimated blood loss at surgery and ruptured ectopic pregnancies requiring a blood transfusion, patient satisfaction) will follow a similar pattern although the type of regression model will be tailored for the specific outcome measure (e.g. hierarchical Poisson/linear regression will be used to analyse number of follow-up visits). Regression modelling will also be used to analyse the effect of opening hours and service accessibility on the overall admission rates and other clinical outcomes. Again, the type of regression model will depend on the clinical outcome and opening hours / service accessibility will be treated as exposure variables.

Health Economic analysis

The economic evaluation will comprise two parts:

- a within-study analysis, and
- a longer-term, model based, analysis.

The within-study analysis will focus on the costs and outcomes during the study period and will be based on the data collected during the study. The longer-term model based analysis will supplement the study data with data from the literature, particularly on patient outcomes. These additional data will be used to estimate the cost-effectiveness of different staffing configurations when longer term outcomes are taken into consideration.

In each analysis we will examine the cost-utility of different skill-mix configurations for staffing EPAUs. Outcomes for each analysis will be 1) patient quality of life, measured as quality adjusted life years (QALYs) and 2) admissions avoided.

Costs will be estimated from a societal perspective (capturing costs to the NHS, social services and patients). Results will be reported as the incremental net benefit of the modelled skill-mix configurations, and incremental cost-effectiveness ratios.

Uncertainty will be captured in the analyses through probabilistic sensitivity analysis and reported using cost-effectiveness acceptability curves, showing the likelihood a particular skill-mix model will be cost-effective over a range of values of the societal willingness to pay for a QALY.

In this section, we detail how we will collect and analyse data for the economic evaluation and how this will link with the skill-mix modelling.

Skill-mix model development:

The services delivered by a given EPAU are determined by two broad factors:

- 1. the workforce delivering the required care, and
- 2. the clinical approach used to deliver that care (for example the thresholds for certain tests to be offered may be different even in configurations where the staff make-up is similar).

Using the clinical and operational data collected as part of the cohort study of clinical outcomes, we will identify skill-mix models appropriate for further consideration in a costutility analysis. This first stage of analysis will define appropriate EPAU skill-mix configurations for assessment in cost-utility analysis. The set of alternative staffing configurations will be used to estimate the expected costs of different skill-mix models, based on what is already known about the studied EPAUs. These models will consider both skill-mix and other factors that determine the cost of delivery local services.

The costs for each EPAU to deliver services will also vary according to each configuration as these will be dependent on the make-up of the local workforce as well as the local costs of

premises and equipment. While care pathways may be consistent across the country as a result of the nationally adopted guidelines, the scale and size of each EPAU will be different due to the service requirement of each locality due to population size, epidemiological factors and local socio-economic characteristics (such as ethnicity, levels of deprivation and education). This means that the workforce size and EPAU cost required to meet the service requirement will be locally dependent, and we will account for variation in costs in the analysis.

Within the skill-mix model we will consider the level of consultant presence, as well as the number and grade of other clinical and support staff available. The costs of implementing any configuration will include both the quantity of each skill set (consultant, junior doctor, nurse etc) required and the coverage time for which they are required. Another important factor to consider in skill-mix models will be case mix. A complex case mix may create a workload equivalent to that in a bigger unit with a less complex or complicated case mix.

Development of optimal skill mix model to run

Cost-utility analysis overview:

Using the skill-mix model analysis we will then evaluate the cost utility of the set of identified potentially optimal skill-mix configurations. This analysis will combine the results of the skill-mix modelling configurations (with associated costs), patient outcome data, patient resource use data and data on additional costs to patients, social services and the NHS not already captured in the EPAU unit configuration costs. Results of the economic evaluation will be reported in standard metrics, including:

- The incremental cost-effectiveness ratio (ICER) of an additional admission avoided, (cost per additional avoided)
- The ICER based on quality adjusted life years (cost per QALY gained), and
- the net benefit statistic.

Sensitivity analysis will be used to test assumptions about the model structure, to explore the generalizability of the results and to capture the underlying uncertainty in the sample data. Probabilistic sensitivity analysis will be used to capture the uncertainty arising from the sampled data, with model parameters defined as probability distributions and Monte Carlo simulations used to simulate repeated trials. Structural uncertainty in the model (for example, relating to variability in individual skill-mix configurations or local staff availability) will be explored using one-way and scenario analyses. Additional one and two-way analyses will be used to explore further the generalisability of the results.

Primary within-study analysis

The primary economic evaluation will be a within-study analysis. As described above, in the analysis we will estimate incremental cost-effectiveness ratios for the two main outcomes of interest, patient quality of life (in QALYs) and admission rates. These will be reported together with associated Bayesian credible intervals, based on the data collected in during

the study period. For this analysis data will be drawn as far as possible from the study data. Monte Carlo simulation methods will be used to construct a cost-effectiveness acceptability curve, based on the expected net benefit statistic, to estimate the probability that the intervention is cost-effective for a range of values of societal willingness to pay per QALY. We will also subject the results to extensive deterministic (one, two, and multi-way) sensitivity analysis.

The analysis process will be as follows: Initial data exploration will be conducted using standard frequentist statistical approaches. First we will compare baseline costs and other factors between groups to determine if any of the baseline characteristics predict costs. Where there are differences appropriate methods will be used to standardise/adjust for these. Unadjusted costs and outcomes will be estimated and reported. Regression analyses will be used to adjust for differences in baseline characteristics and adjusted values will also be reported. Estimates of skewness will be calculated for all resource use variables. As resource use data are commonly skewed, appropriate regression methods will be required (eg GLM) to account for this.

We will explore whether there are baseline characteristics across each group that explain differences in costs. This will be used to explain how costs are linked to baseline characteristics and the intervention. This will help us understand skill-mix variation effects holding everything else constant. It can also help us understand what the drivers of patient costs are and whether they are associated with any between group differences. Coefficients and p-values will be reported for each model tested.

Once we have explored the data and assessed for any important difference in baseline characteristics cost-effectiveness analysis can be undertaken. Unadjusted data will be used for the cost-effectiveness analysis. Simulation methods as described by O'Hagan and others²² will be applied. As is common with healthcare data, costs are expected to be skewed due to a small number of patients who typically consume a disproportionately large level of resources. As a result, the assumptions required for standard statistical approaches based on normally distributed data do not hold. A Bayesian parametric approach to analysis of costs will be followed to address concerns arising from the expected non-normality of the data.

Changes in reported anxiety measured using the visual analog scale will also be evaluated. Anxiety measures will be taken at the baseline data collection point, at the end of the initial visit to the EPAU prior to discharge and then at any clinic follow-up appointments. In the absence of an accepted minimally important difference in anxiety scores a standardised scoring based on Cohen effect sizes will be applied, with 0.2 assumed to be 'small' effect size, 0.5 medium effect size and 0.8 a large effect.

Secondary modelling analysis

Additional longer-term modelling will also be undertaken based on the sub-sample of women followed up at 26 weeks gestation or 3 months post-pregnancy loss. For this analysis, a decision analytic model will be developed, based on the sample data. The model will be used to combine all relevant input data on skill mix variation along with patient

outcomes and costs as measured at 26 weeks/3 months. As with the within-study analysis cost-effectiveness results will be reported as a) the incremental cost per QALY gained and b) the incremental cost per admission avoided. Again, we will also report the net-benefit statistic. Uncertainty in the model parameters will be captured by probabilistic sensitivity analyses using Monte Carlo simulations. Overall decision uncertainty will be calculated and presented using cost-effectiveness acceptability curves. Additional one-way, two-way and scenario sensitivity analysis will be undertaken to test assumptions made in the initial model structure (these assumptions are not subject to parameter uncertainty but may influence results).

Analysis of qualitative interview data

The analysis of the qualitative interview data will be carried out using the Framework method²⁴, utilising NVivo software. The Framework method has five stages (1) familiarization, 2) identifying a thematic framework, 3) indexing; 4) charting, and 5) mapping and interpretation) and allows cross- and between-case analysis. The focus of the analysis will be to examine the range of women's experiences of EPAU services, and to explore how aspects of service provision relate to women's positive and negative experiences. Features of service provision shown to be important in previous research (e.g. choice, empathetic care) will also be included, investigating how women perceive these and how/if these relate to EPAU service configuration.

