2 BACKGROUND AND RATIONALE

There are currently an estimated 200 EPAUs in the UK in NHS hospitals², according to the Association of Early Pregnancy Units (AEPU). EPAUs provide clinical care and support to women presenting with pain and bleeding in the first trimester of pregnancy. The National Service Framework³ recommends that EPAUs should be generally available and easily accessible, set up in a dedicated area in the hospital, with appropriate staffing and ultrasound equipment, as well as easy access to laboratory facilities. There should be direct referral access for GPs, and selected patient groups, such as women who experienced an ectopic or molar pregnancy in the past.

However, there is considerable variation between different units in the levels of access to their services and the levels of care they provide. The best configuration of EPAUs for optimal balance between cost-effectiveness, clinical, service and patient-centered outcomes remains unknown.

The recently published NICE guideline on Ectopic Pregnancy and Miscarriage (CG 154)¹ aimed to establish how different models of care within EPAUs might impact on service outcomes, clinical outcomes and women's experience of care. Fourteen studies were identified. The majority of studies (n=10)^{4,5,6,7,8,9,10,11,12,13} were conducted in the UK. Of the included studies, two were cross-sectional studies^{4,5}, four were observational studies^{6,14,15,16} that compared outcomes before and after establishment of an EPAU, and the remaining studies were descriptive^{7,8,9,10,11,12,13,17}. The quality of evidence was described as low or very low¹.

Evidence from cross-sectional studies showed that in approximately half of the units, ultrasound scans are performed by sonographers only, whilst in less than a quarter of EPAUs, the scanning is done by medical, nursing or midwifery staff^{1,4,5}. In the rest of the units, professionals from different disciplines perform ultrasound scanning. Regarding access to services, all units accept patients referred from other healthcare professionals, whilst only 51% of units accept self-referrals, and the majority of units (70%) provide a weekday service only^{1,4,5}. There is a paucity of data regarding the best indicators for clinical and service outcomes, whilst women's views and experience of care were only included in two studies^{1,11,13}.

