3.2 Secondary Objectives

- To test the hypothesis that increased consultant presence in EPAUs improves other clinical outcomes, including number of follow-up visits, non-diagnostic ultrasound scans, negative laparoscopies and ruptured ectopic pregnancies requiring blood transfusion.
- To assess the effect of variations in opening hours and service accessibility on the overall admission rates and other clinical outcomes.
- To determine the optimal skill-mix to run an effective and efficient EPAU service.
- To examine the cost-effectiveness of different skill-mix models in EPAU.
- To explore patient satisfaction with the quality of care received in different EPAUs.
- To make evidence-based recommendations about the future configuration of EPAUs in the UK.

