7 ELIGIBILITY CRITERIA

7.1 Inclusion Criteria

(i) Cohort study of clinical outcomes

All pregnant women (16 years of age and over) attending Early Pregnancy Assessment Units because of suspected early pregnancy complications.

- (ii) Health economic evaluation
- (iii) Patient satisfaction survey
- (v) Qualitative interviews with service users

Pregnant women (16 years of age and over) attending Early Pregnancy Assessment Units because of suspected early pregnancy complications who agree to sign a written consent to participate.

(vi) Hospital emergency care audit
All women attending hospital emergency service because of early pregnancy complications over a period of three months.

(iv) Staff survey

All members of staff directly involved in providing early pregnancy care who agree to sign a written consent form to participate.

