Women who have taken part in the (iv) patient satisfaction survey and who have consented to being re-contacted in relation to a telephone interview will form the sampling frame for the qualitative interviews. A purposive, maximum-variation sample will be constructed to include women with different outcomes (e.g. ongoing pregnancy, miscarriage, ectopic pregnancy), different levels of reported satisfactions (e.g. above and below average satisfaction on SAPS), and experiences of EPAUs in different regions and with different service configurations. When re-contacted and invited for interview, women will have the opportunity to consent to an interview or to decline.

(vii) Hospital emergency care audit

Routine data for all women attending hospital emergency service due to early pregnancy complications will be collected over a period of three months at the time of site initiation. We

will collect data about the total number of attendances to EPAU and A&E departments. We will also collect data about the total number of emergency admissions, emergency operations and their outcomes, number of women receiving blood transfusions and number of admissions to intensive care units. Women will not be asked to consent to participate in this arm of the study.

Table 2 contains a summary of the different data strands of study, including types of different questionnaires and their timings.

Data strand	Data collection tool	Data source When collected		Type of data
Cohort study of clinical outcomes	CRF	All women attending the service	At site initiation until 150 women have provided complete data	Anonymised
Health economic evaluation	EQ-5D 5L Q VAS-A VAS-A EQ-5D 5L Q	Women attending the service who consent	Upon arrival at EPAU After initial clinical assessment During follow-up visit, prior to and following clinical assessment 2 weeks post-discharge	Identifiable
	CSRI Q EQ-5D 5L Q		3 months post-discharge	
Patient satisfaction survey	SAPS Q LMUP Modified Newcastle Q	Women attending the service who consent	2 weeks post-discharge	Identifiable
Qualitative interviews wih service users	Interviews	Women attending the service who consent (purposive sample of 40)	Following analysis of clinical outcomes & SAPS Q	Identifiable
Hospital emergency care audit	Routine hospital data	All women admitted to hospital	Prospective for 3 months after site initiation	Anonymised

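### The opening-hours analysis of admissions names no population; read in place it uses women who reached the EPAU, a group that opening hours help to select, and the audit that could supply a hospital-wide rate is not linked to it and is described inconsistently

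*Protocol*

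**What the plan says.** The effect of opening hours is a stated secondary objective (Protocol section 3.2): "To assess the effect of variations in opening hours and service accessibility on the overall admission rates and other clinical outcomes". Section 9.3.2 carries it into the analysis with regression models to "analyse the effect of opening hours and service accessibility on the overall admission rates and other clinical outcomes", in which "opening hours / service accessibility will be treated as exposure variables". Neither place names the data strand, the population or the denominator.

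The cohort study in section 7.1 consists of "All pregnant women (16 years of age and over) attending Early Pregnancy Assessment Units because of suspected early pregnancy complications". The audit is a separate strand. Section 7.1 defines it as "All women attending hospital emergency service because of early pregnancy complications over a period of three months", and the text of section 8.2 agrees: "Routine data for all women attending hospital emergency service due to early pregnancy complications will be collected over a period of three months". That text also plans counts of EPAU and A&E attendances and of emergency admissions. Table 2, in the same section, gives the audit's data source as "All women admitted to hospital".

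Section 9.1 comments on the audit only to say that three months should give enough numbers for rare outcomes, with negative laparoscopies, transfusions and ITU admissions as examples. Section 9.3 does not mention the audit. On how far opening varies, section 2 reports from earlier surveys that "the majority of units (70%) provide a weekday service only" and that 51% accept self-referrals.

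**The concern.** Opening hours act partly by deciding where a woman with bleeding or pain presents. If the unit is closed she may go to A&E and be admitted from there without ever entering the EPAU cohort. An admission rate among EPAU attenders therefore leaves out the very admissions that restricted opening might cause. Patient-level covariates cannot restore them, because those women have no record in the cohort.

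The consequence is that a unit with short hours may look better, or worse, than its hospital's true record. The protocol intends to recommend how EPAUs should be configured, so an unlabelled estimate of this kind could be read as evidence on opening hours when it describes only the women who got in.

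The conflict over the audit adds to this. A site that follows Table 2 records admitted women only, and those records alone cannot give an admission rate. A later analysis plan cannot recreate non-admitted attenders who were never recorded.

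**Working it through.** The protocol states no figure for this analysis, so there is none to reproduce. Its sample size concerns the consultant-presence comparison and does not bear on this point.

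**Which population?** Section 9.3.1 fits patient-level models with women clustered within EPAUs. Section 9.3.2 says the secondary analyses follow a similar pattern and then turns to opening hours without naming another source. The pilot table in section 2 also expresses admissions per EPAU attendance. The natural reading is the EPAU cohort.

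**How large could the distortion be?** All risks and bypass shares below are assumptions; the documents give none. In each case the hospital-wide risk is the same in both types of unit, so the true odds ratio (OR, short versus long hours) is 1.00.

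*Scenario A.* Risk is 5% on weekdays and 10% at weekends, with equal attendance each day. Weekend women at weekday-only hospitals never reach the EPAU.
- Seven-day unit: (5/7) × 5% + (2/7) × 10% = 6.43%.
- Weekday-only unit, cohort: 5.0%.
- OR = (0.05/0.95) / (0.0643/0.9357) = 0.77.

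*Scenario B.* Hospital-wide risk R = 6%. A share q of the women who will be admitted bypass the EPAU in short-hours units. The cohort rate is R(1 − q)/(1 − Rq), and the OR reduces to 1 − q.

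| q | cohort rate | OR |
|---|---|---|
| 10% | 5.4% | 0.90 |
| 20% | 4.9% | 0.80 |
| 2/7 | 4.4% | 0.71 |
| 40% | 3.7% | 0.60 |

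*Scenario C.* A share k of all women bypass, with admission risk RR times that of the women who attend. The cohort rate is R/(k × RR + 1 − k), again with R = 6%.
- k = 10%, RR = 2: 0.06/1.10 = 5.45%, OR 0.90.
- k = 20%, RR = 3: 0.06/1.40 = 4.29%, OR 0.70.
- RR = 1: 6.0%, OR 1.00, no bias.
- RR below 1 makes the divisor less than 1, so the OR exceeds 1 and the bias changes direction.

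**Does the audit denominator help if women are counted twice?** Take scenario A with 100 women per hospital: 71.43 on weekdays (3.571 admitted) and 28.57 at weekends (2.857 admitted, 25.71 not). Suppose that, where the EPAU is shut, some non-admitted weekend women are seen again in the EPAU, and that none is admitted on return. The comparison is the seven-day unit at 6.43%.

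| Non-admitted weekend women who return | EPAU cohort only | EPAU + A&E visits |
|---|---|---|
| none | 5.0%, OR 0.77 | 6.43%, OR 1.00 |
| half | 3.571/84.29 = 4.2%, OR 0.64 | 6.43/112.86 = 5.7%, OR 0.88 |
| all | 3.571/97.14 = 3.7%, OR 0.56 | 6.43/125.71 = 5.1%, OR 0.78 |

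Summed visits do not remove the bias when women return, but in each row they are closer to 1.00 than the cohort. Counting women rather than visits gives 1.00 in every row.

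**The case against.** Several stronger readings are tempting, and the documents do not support them.

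- *That the protocol restricts this analysis to EPAU attenders.* It does not say so. The objective speaks of *overall* admission rates, which could mean hospital-wide, and section 12 defers detail to an analysis plan that is not shown. This stands. But the hospital-wide reading needs the attendance denominator that Table 2 puts in doubt, so the ambiguity matters either way.
- *That the audit is reserved for rare outcomes or goes unused.* Section 9.1 makes a remark about power and gives examples; it reserves nothing. What can be said is that section 9.3 does not link the audit to this objective.
- *That weekday/weekend adjustment deals with it.* In scenario A, restricting to weekdays gives an OR of 1.00, section 9.1 requires at least seven days of data, and section 9.3.1 allows confounder adjustment. But a weekday-only unit has no weekend attendances to adjust with. A weekday comparison describes care while the unit is open, not the effect of its being closed.
- *That EPAU plus A&E attendances is simply the right denominator.* These are visits, and the pilot shows 26.6% to 44.4% of EPAU attendances were follow-ups. Double counting can bring back much of the bias, as shown above. This stands and shapes the fix.
- *That Table 2 leaves the audit with no denominator.* The section 8.2 text separately plans attendance totals, and only one table cell disagrees. The correction is small, but the cell tells sites whom to record.

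**Conclusion.** The concern holds as a gap in specification with a plausible selection bias behind it. Section 9.3.2 does not name the population for the opening-hours analysis of admissions. Its natural reading conditions on EPAU attendance, which the exposure can influence, and the audit that could supply a hospital-wide rate is neither linked to the objective nor described consistently.

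The size and direction cannot be computed from the documents. The illustrative ORs run from 0.56 to 1.00 with no true effect, and would exceed 1 if women who bypass the unit are at lower risk. A reader might infer from the 0.77 that the analysis would reverse the true answer; that figure rests on assumed risks and shows only that bias of this order is possible. The 70% weekday-only figure comes from earlier surveys, not from the participating units.

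A reader might also infer that the consultant-presence comparison is confounded. That would require presence to vary with opening hours among the selected units. Section 9.1 indicates that units were selected by a similar approach, with consultant presence and weekend availability among the key factors, and section 9.3.1 plans adjustment for confounders. The documents do not establish that problem.

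**What to change.** In section 9.3.2, state that the effect of opening hours and accessibility on admissions will be estimated from the audit:

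- numerator: hospital-wide emergency admissions for early pregnancy complications;
- denominator: EPAU plus A&E attendances, counted as women or first attendances where sites can supply them, and otherwise with a sensitivity analysis for women counted in both places;
- model: unit-level binomial, allowing for variation between units;
- reporting: beside the EPAU-cohort estimate, labelled as conditional on EPAU attendance.

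Reconcile the audit row of Table 2 with section 7.1 and the section 8.2 text, so that attenders who are not admitted are recorded. Repeating the consultant-presence comparison on the hospital-wide outcome is optional.

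The cost is a few sentences and one table cell, since the counts are already planned. The downside is that aggregate, anonymised data allow little case-mix adjustment and may count some women twice, which is why both estimates should be shown.
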